first week of entering the Pain Treatment Unit located in the Johns Hopkins Hospital. The goals of the study are to collect initial feasibility and efficacy data to support a NIH grant application.

Study Enrollment: During the first week of their residential stay, patients who meet initial eligibility criteria will be informed of the study by their attending physician or other clinic staff member. Patients who are interested in the study will review and sign the informed consent with a trained study staff member before completing the Screening. To increase generalizability, the Screening process will be very limited and restricted to collecting baseline data regarding opioid withdrawal severity and information to characterize the sample. Participants will also be asked to provide authorization for the study to access their medical records to allow documentation of additional concurrent medications and retention in treatment.

Standard of Care Taper Procedures:

- This study will be run concurrent with the standard taper that is administered in the Pain Treatment Unit. The study will not dictate the terms of the taper, however (if our hypothesis is correct) it is possible that the taper may occur more quickly in patients who are treated with buspirone. Information regarding the taper will be retrieved from the medical records and evaluated as outcome data.
- The tapering protocol is individualized to the patient but follows the same standard rationale. Patients are generally stabilized on their admitting medications to ensure they have informed the staff their correct usage. They are then converted to a long-acting formulation such as Oxycontin (if not already on one) and a standing schedule of dosing is implemented (e.g., q6 hours). In most cases, the opioid dose is decreased by 10-20% every 3 days, and withdrawal symptoms and pain are monitored. The speed and magnitude decrease of the taper is adjusted based upon the results of those ongoing assessments in order to optimize patient participation in the treatment plan. The goal is to completely taper the patient off opioids by the end of 28 days, though this may vary depending on the individual circumstances of the patient. Additional PRN concomitant medications are also made available via standing orders to help manage symptoms of withdrawal (e.g., nausea, diarrhea, muscle aches and pains). Medications are available upon patient request.

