- Study medication will be prescribed for thrice-daily administration and will be managed independent of PRN medications.

Study Procedures:

- Participants who are enrolled into the study will be randomized (stratified by sex, current morphine equivalent dose ($>100\text{mg}/\leq 100\text{mg}$), and Brief Pain Inventory Severity Scale ratings ($<7/\geq 7$)) to receive double-blind dose of buspirone (15mg, TID) or placebo. Buspirone will be purchased commercially and over-encapsulated to support blinding. In the event a participant leaves the unit prematurely (e.g., before completing the buspirone taper) he or she will be abruptly discontinued from buspirone.
- Participants will be asked to complete daily self-report ratings of opioid withdrawal severity (such as the Subjective Opioid Withdrawal Scale; SOWS) and to complete an exit survey that indicates whether they would recommend the medication to another person and the degree to which they believe the study medication helped them to successfully taper down on opioids and to which it suppressed their withdrawal symptoms.
- Participants will be permitted to stop taking the study medication at any time period and adherence will be collected and analyzed as a measure of acceptability.

- We will ask participants to refrain from requesting additional concomitant medications to help manage withdrawal symptoms until absolutely necessary. However, participants' requests for additional concomitant medication will be honored, and the day on which additional medication was requested will be recorded as a measure of efficacy (with the hypothesis that buspirone may delay the need for additional medications). Concomitant medications will be administered as part of the standard clinical practice and will not be provided by the study, though data regarding medication use will be collected for study outcome analyses. We believe this is the best approach for this initial study, as we cannot yet be certain that buspirone will reduce the severity of the withdrawal syndrome.

b. Study duration and number of study visits required of research participants.

Participants will be enrolled for the duration of their residential stay or 28 days, whichever comes first.

c. Blinding, including justification for blinding or not blinding the trial, if applicable.

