- b. Justification and safety information if FDA approved drugs will be administered for non-FDA approved indications or if doses or routes of administration or participant populations are changed.

Buspirone is FDA-approved for the treatment of anxiety disorder and can be prescribed off-label for other indications. Consistent with our study procedures, the FDA permits a maximum of 60mg to be administered per day in divided doses.

- c. Justification and safety information if non-FDA approved drugs without an IND will be administered.

N/A

7. Study Statistics (Partially Blinded)

a) Primary outcome variable.

i. Feasibility

- a. Participant retention in treatment, evaluated as a) last day in the study and b) being present on the final day of the study

ii. Initial Efficacy

- a. Withdrawal symptom suppression, measured through daily self-report ratings of withdrawal on the Subjective Opiate Withdrawal Scale (SOWS)

b) Statistical plan including sample size justification and interim data analysis.

- a) Sample size: This is a pilot study to support an R01 trial. A power analysis using G-power, evaluating an independent groups t-test of area-under-the-curve (AUC) values from the SOWS, with alpha set to 0.05, revealed that 12 participants per group would yield 60% (moderate) power to detect a large (0.80) effect. We believe this will provide sufficient data to support an R01 study evaluation.

- b) Statistical Plan. Given the small sample size and low perceived risk, no interim data analyses will be conducted.

1. Feasibility

- i. Patient retention in treatment will be compared across groups using independent groups t-tests for continuous and chi-squares for dichotomous outcomes. Regressions factoring group, baseline opioid dose in morphine equivalents, pain severity ratings from the Brief Pain Inventory, and number of concomitant medications, and study medication adherence (% prescribed doses) will be used to determine the degree to which group assignment predicted being retained on the final scheduled day (Logistic) and final day in treatment (Linear).

2. Initial Efficacy

- i. Withdrawal symptom suppression will be compared across groups using area-under-the-curve (AUC) analyses.

c) Early stopping rules.

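### The SOWS AUC comparison uses no baseline covariate; a prespecified ANCOVA on baseline SOWS is a possible, conditional gain in precision, not the repair of an error

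*Combined protocol and SAP*

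**What the plan says.** - **Efficacy analysis (section 7 b) 2).** "Withdrawal symptom suppression will be compared across groups using area-under-the-curve (AUC) analyses". No model or covariate is named, and the AUC is not defined.
- **Sample size (section 7 b) a)).** The power calculation is described as "evaluating an independent groups t-test of area-under-the-curve (AUC) values from the SOWS", with alpha 0.05, 12 per group, an effect of 0.80 and 60% power. It does not say whether the test is one-sided or two-sided.
- **Baseline data (section 4a, Study Enrollment).** Screening is "restricted to collecting baseline data regarding opioid withdrawal severity and information to characterize the sample". The instrument is not named there. The SOWS appears as an example of the daily rating in section 4a, Study Procedures, and as the efficacy measure in section 7 a).
- **Randomisation (section 4a, Study Procedures).** "Participants who are enrolled into the study will be randomized (stratified by sex, current morphine equivalent dose", and the sentence goes on to add Brief Pain Inventory severity. Baseline withdrawal is not a stratification factor.
- **Retention (section 7 b) 1).** "Patient retention in treatment will be compared across groups using independent groups t-tests for continuous and chi-squares for dichotomous outcomes". The plan then adds further models: "Regressions factoring group, baseline opioid dose in morphine equivalents, pain severity ratings from the Brief Pain Inventory", together with the number of concomitant medications and adherence to study medication. No such model is listed for the SOWS.

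**The concern.** Baseline withdrawal severity is one of the few things that Screening collects, and no listed analysis uses it. The SOWS AUC is the only efficacy outcome in section 7, and its estimate is meant to support an R01 application. With 12 per group that estimate will be imprecise: the expected 95% confidence interval half-width is about 0.84 SD, wider than the planned effect of 0.80. If baseline SOWS predicts the AUC, an unadjusted comparison leaves in the error term variation that could be removed without enrolling anyone.

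Prespecification matters too. A one-line plan leaves the choice between an adjusted and an unadjusted result open until the data have been seen.

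**Working it through.** **Inputs from section 7 b).** n = 12 per group (N = 24), alpha 0.05, effect d = 0.80 in units of the unadjusted SD, stated power 60%.

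**Assumed, not in the documents.** r, the within-group correlation of baseline SOWS with the AUC, shown over a range; and 24 comparable AUCs.

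**Step 1: reproduce the plan's figure.** For the unadjusted t-test, the noncentrality is d × √(n/2) = 0.80 × √6 = 1.96 on 22 degrees of freedom.
- One-sided 0.05: power 60.0%. This matches the stated 60%.
- Two-sided 0.05: power 46.6%. This does not match.

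Both readings are carried forward because the plan does not state sidedness.

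**Step 2: ANCOVA with one baseline covariate.** The residual variance is multiplied by (1 − r²). Chance imbalance in the covariate multiplies the variance of the group difference by an expected 1 + 1/(2n − 4) = 1 + 1/20 = 1.05. The noncentrality is therefore 0.80/√(1 − r²) × √(6/1.05), on 21 degrees of freedom.
- r = 0: 0.80 × 2.39 = 1.91
- r = 0.3: 1.91/√0.91 = 2.00
- r = 0.5: 1.91/√0.75 = 2.21

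| Analysis | Power, one-sided | Power, two-sided |
|---|---|---|
| Unadjusted t-test | 60.0% | 46.6% |
| ANCOVA, r = 0 | 58.1% | 44.6% |
| ANCOVA, r = 0.2 | 59.6% | 46.1% |
| ANCOVA, r = 0.3 | 61.6% | 48.1% |
| ANCOVA, r = 0.5 | 68.8% | 55.8% |
| ANCOVA, r = 0.7 | 82.8% | 72.4% |

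Simulation with 40,000 trials at each of these r values agreed within about 1 point.

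**Step 3: break-even.** Setting ANCOVA power equal to t-test power gives r = 0.225 one-sided and 0.228 two-sided, so about 0.23. Below that, adjusting loses a little power.

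**Step 4: width of the interval.** The expected 95% half-width is 0.84 SD unadjusted. With ANCOVA it is 0.86, 0.82 and 0.74 SD at r = 0, 0.3 and 0.5. At r = 0.5 the ratio is 0.744/0.837 = 0.889, so the interval is 11% narrower. The equivalent unadjusted sample is 12/(0.75 × 1.05) = 15.2 per group.

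**The case against.** **The gain may be small or absent.** Section 4a, Standard of Care Taper Procedures, gives reasons to expect a low r. "Patients are generally stabilized on their admitting medications" before the taper, which may narrow the spread of baseline scores. "The speed and magnitude decrease of the taper is adjusted based upon the results of those ongoing assessments", and PRN medication is available on request, so care responds to symptoms during follow-up. At r = 0.3 the gain is only about 1.6 points of power, and the half-width, at 0.82 SD, still exceeds 0.80. This stands. The r = 0.5 case is an illustration, not an expectation.

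**The covariate is not established.** Screening names no withdrawal instrument, and its timing relative to the first dose is not stated. This stands, and the fix is conditional on it.

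**The outcome is not defined.** The plan does not say whether the AUC is raw or baseline-corrected, what period it covers, or how early discharge is handled. If it is baseline-corrected, baseline is already partly used. This also stands: an AUC definition has to come first, and ANCOVA does not supply one or deal with unequal follow-up.

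**The plan may hold more than is shown.** The heading of section 7 describes it as partially blinded, so silence on covariates may not be the full plan. Nothing in the text settles this.

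**A pilot of 24 may reasonably use a t-test.** This is true. What remains is an uneven trade: at most about 2 points lost at r = 0, against about 9 gained at r = 0.5, for a short change of wording.

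**Conclusion.** The point holds as an optional improvement. Its size runs from a loss of about 2 points of power at r = 0, through a gain of about 1.6 points at r = 0.3, to about 9 points at r = 0.5, whichever sidedness applies. It rests on an assumed r, on d = 0.80 with 12 per group, and on 24 comparable AUCs.

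A reader might infer four stronger things that the documents do not support:
- **That the planned t-test is wrong or biased.** It is valid and unbiased under randomisation.
- **That ANCOVA will improve precision.** It does so only if r exceeds about 0.23, and no passage gives r.
- **That 46.6% contradicts the stated 60%.** Sidedness is not stated, and 60% is exact for a one-sided test. Stating the sidedness is a separate matter.
- **That the SOWS was singled out for a weaker analysis than retention.** Retention is also compared unadjusted first; the difference is only the added regressions.

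On the stratification factors, a test that ignores them is somewhat conservative if they predict the AUC. The size of that effect cannot be given, because it depends on the prognostic strength of the factors, the block size and the stratum frequencies, none of which the documents report.

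**What to change.** In section 7 b) 2:

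1. Confirm that the Screening withdrawal measure is the SOWS and is taken before the first dose. If either condition fails, keep the t-test as the main analysis.
2. If both are met, prespecify an ANCOVA of SOWS AUC on group and pre-dose baseline SOWS as the main analysis. Report the adjusted difference with its 95% confidence interval, and the unadjusted t-test as supportive.
3. Add one sensitivity analysis that also includes the three stratification factors as main effects, because baseline SOWS alone does not account for the stratified randomisation.
4. Use baseline covariates only. Concomitant medications and adherence, which appear in the retention regressions, are measured after randomisation and should not enter the SOWS model.

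**Cost.** One or two sentences of analysis wording, and no new data if the Screening measure is the SOWS. The main model uses 1 degree of freedom for the covariate and loses about 2 points of power if r = 0. The sensitivity model uses 4, leaving 24 − 2 − 4 = 18 residual degrees of freedom. Defining the AUC and handling unequal follow-up are further work that this change does not cover.

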Participants will be discharged from the study if they leave the residential unit against medical advice, request to be removed from the study, begin taking a medication that is contraindicated with participation, are diagnosed with a contraindicated condition, express suicidal thoughts, or if new information becomes available to suggest this study may cause them more than minor harm.

8. Risks

- a. Medical risks, listing all procedures, their major and minor risks and expected frequency.

Buspirone (Buspar) is an oral tablet that is FDA-approved for the treatment of anxiety and prescribed off-label for the treatment of depression. It has been prescribed at doses up to 90mg/day for depression. The maximum dose provided to participants in this study (45mg/day) is well within the range of approved doses and is below the maximum dose recommended for the treatment of anxiety (60mg/day). Buspirone is rated as pregnancy category B, indicating that animal studies have not indicated a unique risk of buspirone on the

developing fetus but that controlled human studies have not yet been conducted. We will exclude all women who are pregnant or breastfeeding from participating. When administered orally (as proposed here) buspirone effects peaks in 40-90 minutes. It has 90% bioavailability and 86% protein binding. It is subject to extensive first-pass metabolism by the P450 CYP3A4 enzymes, and produces active metabolites. The elimination half-life is 2-3 hours, and this is prolonged in patients with impaired hepatic or renal function.

Buspirone is excreted in both fecal (18-38%) and renal (29-63%) waste, though renal excretion is primarily as metabolites. Buspirone is contraindicated with severe hepatic or renal impairment, and has several severe drug interactions with alcohol, MAOIs, and grapefruit juice (all of which will be excluded).

Recognized side effects include nausea (8%), dizziness (12%), headache (6%), somnolence (10%), and feeling nervous (5%). Potential serious side effects include congestive heart failure (less than 0.1%), myocardial infarction (less than 0.1%), and cerebrovascular accident (less than 0.1%).

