All study events will be monitored during weekly meetings between the study investigators and we will follow all IRB guidance and recommendations regarding the reporting of unanticipated problems of study deviations. All such problems and deviations will be documented and if they do not meet the criteria for immediate reporting, they will be submitted to the IRB as part of the continuing review (or when otherwise requested).

- d. Legal risks such as the risks that would be associated with breach of confidentiality.

We do not believe this study poses any legal risks associated with breach of confidentiality.

- e. Financial risks to the participants.

Participants will not incur any cost for study participation. All study medications will be provided to them at no cost.

9. Benefits

- a. Description of the probable benefits for the participant and for society.

This study will collect pilot data to support an NIH grant application to evaluate bupirone as an adjunctive medication to help suppress and/or manage symptoms of opioid withdrawal during clinically-indicated tapering. This approach is grounded in sound preclinical mechanistic data and results from this line of research has the ability to make a new medication immediately available for wide-spread use to help combat and address the opioid use disorder epidemic and need to taper patients down from high doses of opioid medications for pain control.

10. Payment and Remuneration

- a. Detail compensation for participants including possible total compensation, proposed bonus, and any proposed reductions or penalties for not completing the protocol.

Participants will be paid \$10 a day and a \$120 completion bonus at the end of the study, for a total potential earning of \$400. Payments will be made contingent upon completion of withdrawal rating measures only and not medication adherence, to prevent patients from continuing to take the medication for the compensation even if they experience untoward effects from doing so. All payments will be made via check to the participant or on a reloadable credit card that will be provided to patients upon discharge from the unit.

11. Costs

- a. Detail costs of study procedure(s) or drug (s) or substance(s) to participants and identify who will pay for them.

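### Side effects are neither systematically asked about nor summarized by arm, and the symptom behind a PRN request is not recorded, so a request for drug-caused nausea would count against buspirone unseen

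*Combined protocol and SAP*

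**What the plan says.** - **Known effects (Section 8a):** "Recognized side effects include nausea (8%), dizziness (12%), headache (6%), somnolence (10%), and feeling nervous (5"%). Three serious effects, each below 0.1%, follow.
- **What participants report (Section 4a, Study Procedures):** daily withdrawal ratings, and an exit survey on recommending the drug, help with the taper and suppression of withdrawal. No side-effect item is named.
- **PRN medication (Section 4a, Standard of Care Taper Procedures):** available on request to "help manage symptoms of withdrawal (e.g., nausea, diarrhea, muscle aches and pains").
- **Use of requests (Section 4a, Study Procedures):** "the day on which additional medication was requested will be recorded as a measure of efficacy". Medication use is also collected. The symptom that prompted a request is not mentioned.
- **Outcomes (Section 7):** retention, and "Withdrawal symptom suppression, measured through daily self-report ratings of withdrawal on the Subjective Opiate Withdrawal Scale (SOWS"). There is no side-effect or tolerability outcome and no by-arm table of side effects.
- **Partial safeguards:** the reason for a refused dose is documented and classed as primary outcome data (Section 6a). Adherence is analyzed as acceptability (Section 4a). Intolerance is a ground for removal (Section 4f). Adverse effects lead to a decision made with the study physician (Section 8b). Section 8c adds: "All study events will be monitored during weekly meetings between the study investigators".

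**The concern.** Every safeguard in the plan is triggered by a refused dose, an exit or a volunteered complaint. A participant who has side effects, says nothing and takes every capsule leaves no trace in the data. The plan foresees such people: Section 10 separates payment from adherence so that nobody keeps taking the drug for the money despite ill effects.

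Nausea makes this more than a reporting gap. The plan lists it both as an effect of buspirone and as a symptom of withdrawal. If buspirone causes nausea and the participant asks for something to treat it, the day of that request is logged as efficacy data. The drug given can be found in the chart, but nothing says the reason will be. The request counts against buspirone and cannot later be picked out.

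The pilot exists to support a larger grant application. As written, it could not report how many participants in each arm had each of the effects its own risk section names.

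**Working it through.** **1. Arm size.** Section 7b, "evaluating an independent groups t-test of area-under-the-curve (AUC) values from the SOWS", "with alpha set to 0.05", states that "12 participants per group would yield 60% (moderate) power to detect a large (0.80) effect". By the noncentral t distribution, n = 12 per group and d = 0.80 give 60.0% power one-sided and 46.6% two-sided. The stated figure therefore reproduces as a one-sided test. The plan does not state sidedness; that is a separate matter, and only n = 12 is used below.

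**2. Where the texts overlap.**

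| Symptom | Side effect in 8a | Withdrawal symptom treated with PRN in 4a |
|---|---|---|
| Nausea | yes (8%) | yes |
| Dizziness | yes (12%) | not named |
| Headache | yes (6%) | not named |
| Somnolence | yes (10%) | not named |
| Feeling nervous | yes (5%) | not named |

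Only nausea appears in both lists, so only nausea is carried forward.

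**3. Expected drug-caused nausea among 12 on buspirone.** With drug-caused rate p, expected cases = 12p, and P(at least one) = 1 - (1 - p)^12.

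- p = 0.08 (all of the listed rate is due to the drug): 12 x 0.08 = 0.96; 1 - 0.92^12 = 0.63.
- p = 0.04 (half of it, an assumption): 12 x 0.04 = 0.48; 1 - 0.96^12 = 0.39.
- p = 0 (no excess over placebo): 0 cases; probability 0.

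Section 8a gives no placebo rates. Section 6a cites an evaluation of 700 patients at a mean of 20mg with side-effect rates no different from placebo. This trial goes to 45mg daily, so that evaluation does not settle p, but the lower end of the range cannot be dismissed.

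One participant is 1/12 = 8.3% of the arm. A nausea request moves that participant's time to first request only if it comes before any other request.

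**4. What asking would deliver.** If an effect were asked about and seen in 0 of 12, the one-sided 95% upper limit would be 1 - 0.05^(1/12) = 0.22. Exact power of Fisher's test (two-sided 0.05, 12 v 12; placebo rates assumed) is:

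- 8% v 0%: 0.2%
- 30% v 5%: 16%
- 50% v 5%: 59%

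The data would support counts and intervals, not tests.

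**The case against.** The strongest reply is that the plan already gathers tolerability data and that little is at stake for efficacy. Much of this stands.

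- **A reader might infer that the plan collects nothing on tolerability.** It does. Refusal reasons, adherence, removals for intolerance and the weekly review allow a crude comparison between arms. The gap is narrower: side effects in people who keep taking every dose. Section 7 also plans no analysis of the refusal reasons.
- **A reader might infer that nervousness is miscounted as withdrawal too.** The documents do not show this. The SOWS items are not reproduced. The withdrawal items quoted in Section 3 from an earlier buspirone study include restlessness, but neither nervousness nor nausea.
- **A reader might infer that the bias must run against buspirone.** That holds for a nausea request, but not overall. Somnolence, listed at 10%, could lower restlessness ratings or requests for sleep medication, which would favor buspirone.
- **A reader might infer that the SOWS comparison is invalid.** It is not. Randomization means that it estimates the net effect on rated symptoms, whatever their cause. Because the scale's content is not in the documents, I put no figure on any dilution.

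It is also fair to say that time to first request, though named as evidence of efficacy in the Abstract, is not among the Section 7 outcomes.

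The objection does not answer two points: side effects in adherent participants are not solicited, and the symptom behind a request is not recorded. Neither can be reliably recovered afterwards.

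**Conclusion.** The point holds in a limited form. The plan does not systematically ask about side effects and plans no by-arm summary of them. A PRN request for drug-caused nausea would count against buspirone without being identifiable.

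If the whole of the listed 8% is drug-caused, about 1 of 12 would be expected, with a 63% chance of at least one; the drug-caused excess may be near zero. This assumes 12 participants on buspirone, independent participants, and that the rate in Section 8a applies to this dose and population.

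The SOWS AUC analysis is not undermined. What is lost is descriptive side-effect information for the larger grant and the ability to interpret the request measure. The change is worth making because it is cheap and must be made before data are collected.

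**What to change.** - **Section 4a:** add to the daily rating form a short checklist of the five effects in Section 8a and one open question. For each PRN request, record the drug and the symptom it was requested for.
- **Section 7:** add a descriptive by-arm table of participants with each side effect, refusals and discontinuations for side effects, and PRN requests by symptom.

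I would not add an analysis of time to first request that drops requests attributed to a side effect. Deciding whether nausea during a taper comes from the drug or from withdrawal is a subjective judgment made after randomization, and could itself bias the comparison. Showing requests by symptom and arm lets the randomized groups be compared without that judgment.

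**Cost:** about a minute a day on a form already in use, one field per request and one table. Prompting will raise observed rates in both arms, so they should not be set directly against those in Section 8a. The checklist will not settle the cause of nausea in any one person, and with 12 per arm the table stays descriptive. No dose, schedule or primary analysis changes.
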